16.4. Safety

16.4.1. Analysis Population

The safety population is defined as all subjects who receive at least 1 dose of study treatment.

16.4.2. Methods of Analysis

All AEs, concomitant therapy and procedures, clinical laboratory results, physical examinations, vital signs, and 12-lead ECG readings data will be evaluated for safety.

16.4.2.1. Adverse Events

AEs will be coded using the Medical Dictionary for Regulatory Activities. Only treatment-emergent AEs will be presented in the summary tables. Treatment emergent is defined as having an onset date on or after start of study treatment or having worsened after the start of study treatment.

Subject incidences of all AEs, SAEs, AEs leading to treatment discontinuation and study withdrawal, and other AEs of special interest will be tabulated by system organ class and preferred term in descending order of frequency.

16.4.2.2. Clinical Laboratory Results

Clinical laboratory evaluations include hematology and blood chemistry. Laboratory data will be summarized using shift tables. Each laboratory value for each subject will be flagged as “low,” “normal,” or “high,” relative to the parameter’s normal range. For each parameter, the number (percentage) of subjects experiencing post-Baseline shifts to “low” or “high” based on their minimum or maximum values at any time postdose will be summarized. In addition, a

CONFIDENTIAL

The information contained herein may not be used, disclosed, or published without the written consent of
Biogen MA Inc.

summary of laboratory values categorized based on Common Toxicity Criteria grade will also be generated. Summary statistics for actual values and change from Baseline will also be presented for quantitative laboratory data.

16.4.2.3. Physical Examinations

The analyses of physical examinations will include summary statistics (actual value and change from Baseline for body weight and height) over time by visit.

16.4.2.4. Vital Signs

The analysis of vital signs will focus on clinically relevant abnormalities. The number of subjects evaluated and the number and percentage of subjects with clinically relevant post-Baseline abnormalities will be presented by group.

The definitions of these clinically relevant abnormalities are shown in [Table 5](#).

Table 5: Criteria to Determine Clinically Relevant Abnormalities in Vital Signs

Vital Sign	Criteria for Abnormalities
Temperature	>38°C or an increase from Baseline of $\geq 1^{\circ}\text{C}$
Pulse	>120 bpm or an increase from Baseline of >20 bpm <50 bpm or a decrease from Baseline of >20 bpm
Systolic Blood Pressure	>180 mmHg or an increase from Baseline of >40 mmHg <90 mmHg or a decrease from Baseline of >30 mmHg
Diastolic Blood Pressure	>105 mmHg or an increase from Baseline of >30 mmHg <50 mmHg or a decrease from Baseline of >20 mmHg

The analyses of vital signs will also include summary statistics (actual value and change from Baseline for temperature, pulse, and systolic and diastolic blood pressure) over time by visit.

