5.4.4 Vital Signs

The analysis of vital signs will focus on clinically relevant abnormalities. For each vital sign, the number of subjects evaluated and the number and percentage of subjects with the defined abnormality at any time post-baseline will be presented.

The definitions of these clinically relevant abnormalities are shown in [Table 4](#).

Table 4: Criteria to Determine Clinically Relevant Abnormalities in Vital Signs

Vital Sign	Criteria for Abnormalities
Temperature	>38°C post baseline and an increase from Baseline of $\geq 1^{\circ}\text{C}$
Pulse	>120 bpm post baseline or an increase from Baseline of >20 bpm <50 post baseline bpm or a decrease from Baseline of >20 bpm
Systolic Blood Pressure	>180 mmHg post baseline or an increase from Baseline of >40 mmHg <90 mmHg post baseline or a decrease from Baseline of >30 mmHg
Diastolic Blood Pressure	>105 mmHg post baseline or an increase from Baseline of >30 mmHg <50 mmHg post baseline or a decrease from Baseline of >20 mmHg

The analyses of vital signs will also include summary statistics (actual value and change from Baseline for temperature, pulse, and systolic and diastolic blood pressure) over time by visit.

CONFIDENTIAL

The information contained herein may not be used, disclosed, or published without the written consent of Biogen Idec MA Inc.

	Protocol 109MS310 An Open-Label Study to Assess the Effects of BG00012 on Lymphocyte Subsets in Subjects With RRMS	Final Version 1.0
---	---	--------------------------

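### For pulse and blood pressure, the vital-sign abnormality counts mix values already beyond an absolute limit at Baseline with new ones, and no planned output separates them by subject

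*Protocol*

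**What the plan says.** Protocol 16.4.2.4 says that "the number and percentage of subjects with clinically relevant post-Baseline abnormalities will be presented by group". Its Table 5 defines the low rows as "<50 bpm or a decrease from Baseline of >20 bpm" for pulse, "<90 mmHg or a decrease from Baseline of >30 mmHg" for systolic pressure and "<50 mmHg or a decrease from Baseline of >20 mmHg" for diastolic pressure. The high rows have the same form, with an absolute limit *or* an increase from Baseline.

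SAP 5.4.4 says that "the number of subjects evaluated and the number and percentage of subjects with the defined abnormality at any time post-baseline will be presented". It keeps *or* for pulse and both blood pressures; its low-pulse row reads "<50 post baseline bpm or a decrease from Baseline of >20 bpm". The added words about post-baseline timing say when the reading is taken. They do not require the Baseline reading to have been inside the limit. Temperature is the exception: the SAP changed the Protocol's *or* to *and*, so an unchanged temperature no longer qualifies.

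Both sections also plan by-visit summaries of actual values and changes from Baseline. Neither plans a vital-sign shift table. Laboratory data do get one: Protocol 16.4.2.2 counts the "number (percentage) of subjects experiencing post-Baseline shifts to" low or high. ECG data are also shown as shifts (Protocol 16.4.2.5, SAP 5.4.5).

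**The concern.** A reader of a single-arm safety table wants to know how many subjects went beyond a limit after starting BG00012. The percentage as defined answers a different question: how many were beyond the limit, or crossed a change threshold, at any time after Baseline, wherever they started. Subjects with habitually low pulse or blood pressure can enter the study, because the eligibility criteria in Protocol Section 8 set no numeric pulse or blood-pressure limit and the safety population is everyone dosed. There is no control arm whose percentage would show the pre-existing share. The by-visit summaries describe the group at each visit, so they cannot show which counted subjects were already beyond the limit.

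**Working it through.** **The rule applied to subjects who do not worsen.** The documents give no vital-sign abnormality figure to reproduce, so the first check is logical.

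| Sign | Baseline → post-Baseline | Protocol Table 5 | SAP 5.4.4 |
|---|---|---|---|
| Pulse | 48 → 48 | counted | counted |
| Pulse | 46 → 49 | counted | counted |
| Pulse | 122 → 122 | counted | counted |
| Systolic | 88 → 88 | counted | counted |
| Systolic | 182 → 182 | counted | counted |
| Diastolic | 48 → 48 | counted | counted |
| Diastolic | 106 → 106 | counted | counted |
| Temperature | 38.2 → 38.2 | counted | not counted |
| Pulse (control) | 55 → 55 | not counted | not counted |
| Systolic (control) | 120 → 120 | not counted | not counted |

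**Size: inputs.** From the documents: the limits above, about 200 treated subjects (Protocol 7.1), and nine scheduled post-Baseline readings (Protocol Table 1: Weeks 4, 8, 12, 24, 36, 48, 72 and 96, and final Follow-Up). Assumed, because the documents give no distributions: normal variation, no drug effect, and two scenarios per sign.

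| Sign | Mean (scenario A / B) | Between-subject SD (A / B) | Within-subject SD |
|---|---|---|---|
| Pulse, bpm | 72 / 68 | 8 / 9 | 6 |
| Systolic, mmHg | 118 / 112 | 11 / 11 | 8 |
| Diastolic, mmHg | 74 / 70 | 7 / 7 | 5.5 |

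**Below the low limit at Baseline:** Φ((limit − mean) / √(SD_between² + SD_within²)).

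- Pulse: A, (50 − 72)/√(64 + 36) = −2.20, so 1.4%. B, (50 − 68)/√(81 + 36) = −1.66, so 4.8%.
- Systolic: √(121 + 64) = 13.60. A, −28/13.60 = −2.06, so 2.0%. B, −22/13.60 = −1.62, so 5.3%.
- Diastolic: √(49 + 30.25) = 8.90. A, −24/8.90 = −2.70, so 0.4%. B, −20/8.90 = −2.25, so 1.2%.

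**Row percentages.** 400,000 subjects were simulated per scenario. Each low row was computed as written, then with the absolute limit counted only if it was not already met at Baseline. The change criterion was left alone. Subjects affected = difference × 200.

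| Low row | As written | New breach or change only | Difference (points) | Of 200 |
|---|---|---|---|---|
| Pulse A | 11.68% | 10.69% | 0.99 | 2.0 |
| Pulse B | 21.45% | 17.45% | 4.00 | 8.0 |
| Systolic A | 11.23% | 9.75% | 1.48 | 3.0 |
| Systolic B | 21.48% | 17.20% | 4.28 | 8.6 |
| Diastolic A | 5.23% | 5.02% | 0.21 | 0.4 |
| Diastolic B | 9.19% | 8.40% | 0.79 | 1.6 |

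An independent repeat agreed to within about 0.25 percentage points on every row percentage. In the high rows, pulse and systolic did not change, and diastolic changed by at most about 0.01 points. Of the subjects flagged through a low absolute limit, about 9% to 23% already met it at Baseline.

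**The case against.** Several points on the other side stand.

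- **Labelling.** A reader might infer that the table presents unchanged values as emerging on treatment. The documents do not say so. They count post-Baseline abnormalities and define treatment-emergent only for adverse events (Protocol 16.4.2.1, SAP 5.4.1). The table does what its label says; the difficulty is what the label leaves mixed.
- **Consistency with laboratory data.** A reader might infer that vital signs are treated differently from everything else. That is only partly so. The toxicity-grade summary in Protocol 16.4.2.2, and the liver-test categories and worst-value cut-offs in SAP 5.4.2, also use absolute limits with no Baseline condition. The real difference is that laboratory and ECG data have shift tables as well, and vital signs do not.
- **Removing these subjects from the count.** This looks like the natural remedy, but it would lose real worsening. Systolic 88 to 60 (a fall of 28, not more than 30), pulse 49 to 30 (a fall of 19, not more than 20) and diastolic 49 to 30 (a fall of 19, not more than 20) are counted now only through the absolute limit. An over-inclusive screen is a defensible choice for a safety table.
- **What separation would achieve.** With no drug effect at all, the low-pulse row would still be 10.7% to 17.5% and the low-systolic row 9.8% to 17.2%. Ordinary variation over nine readings produces most flags, and separating by Baseline status does not change that.

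None of this supplies the missing information. No planned output shows, by subject, which flagged values were already beyond the limit at Baseline.

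**Conclusion.** The point holds as a matter of presentation. For pulse, systolic and diastolic pressure, both documents count a subject whose value was beyond an absolute limit at Baseline and is unchanged or better afterwards. The single-arm percentages therefore combine pre-existing and new findings.

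The documents cannot settle the size. Under the assumptions shown, it is about 2 to 9 of 200 subjects in the low-pulse and low-systolic rows, 0.4 to 1.6 in the low-diastolic row, and essentially none in the high rows. The upper figures depend on the lower assumed means and, for pulse, the wider assumed between-subject spread. It would be wrong to carry 2 to 9 across to every row.

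A descriptive safety table is affected. The primary endpoint, the sample size and the decision rules are not. The improvement is worthwhile but small.

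**What to change.** In SAP 5.4.4, keep the criteria and the overall count as they are. Report each absolute-limit row split by Baseline status: limit not met at Baseline (new) and limit already met at Baseline (pre-existing), each with its own number evaluated. A vital-sign shift table, like those planned for laboratory and ECG data, would serve equally well. Subjects who worsen from an already low Baseline then stay counted and visible.

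The cost is one sentence in the SAP and one extra column or table. No new data are needed. The percentage labelled new will be somewhat smaller than the overall figure. A footnote should say that, without a control group, even the new column includes ordinary variation over repeated readings.

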16.4.2.5. ECG Data

A listing of subjects with abnormal ECG status will be presented. Changes from Baseline in ECG will be summarized using shift tables. The number and percentage of subjects with shifts to categorical values (abnormal, not AE/abnormal, AE) will be summarized.

[figure not shown]
16.5. Clinical Assessments

16.5.1. Analysis Population

The evaluable population for clinical assessments is defined as all subjects who receive at least 1 dose of study treatment and at least 1 measurement for each of the clinical assessments after Baseline.

CONFIDENTIAL

The information contained herein may not be used, disclosed, or published without the written consent of Biogen MA Inc.

16.6. Interim Analyses

Interim analyses may be performed to support regulatory filings and/or publications and will be documented in the Statistical Analysis Plan.

16.7. Sample Size Considerations

The sample size for this study is not based on formal hypothesis testing but on the precision of the estimation of the primary endpoints and the ratios between various ALC subgroups.

For example, the Phase 2 and 3 controlled and uncontrolled efficacy and safety studies in MS, based on data available as of May 2014 from 2470 subjects with at least 1 post-Baseline value from the interim analysis of the Integrated Summary of Safety of Tecfidera, showed that 76% of subjects had all ALC values \geq LLN and 24% had at least 1 ALC value $<$ LLN up to Week 48.

Assuming the same proportion of subjects in this study will have 1 or more ALC values $<$ LLN, it is expected that approximately 137 subjects will have all ALC values \geq LLN and approximately 43 subjects will have at least 1 ALC value $<$ LLN at Week 48, based on a total of 180 evaluable subjects at Week 48. With this sample size, the 90% CIs for the ratio of the 2 subgroups for the change from Baseline at Week 48 in lymphocyte subsets are illustrated below using the scenario of a true ratio of 0.8 (20% decrease) and 0.7 (30% decrease), respectively. When assessing lymphocyte subsets between subjects with at least 2 ALC values $<$ LLN up to the first 48 weeks of treatment versus subjects who have all ALC values \geq LLN throughout the study, the 90% CIs of the ratio would be wider, as historical data suggest that 16% of the patients treated with Tecfidera may have 2 or more ALC values $<$ LLN during the first 48 weeks of treatment.

To allow for a 10% discontinuation rate, a total of 200 subjects are planned for enrollment.

CONFIDENTIAL

The information contained herein may not be used, disclosed, or published without the written consent of
Biogen MA Inc.

Table 6: Sample Size Calculations

Primary Endpoints	SD ¹	Ratio	90% CI for the Ratio Based on N = 180	
			Subjects With At Least 1 ALC <LLN ² vs. Subjects With All ALC ≥LLN ²	Subjects With At Least 2 ALC <LLN ² vs. Subjects With All ALC ≥LLN ²
CD4 T cell count	0.32	0.8	0.73, 0.88	0.71, 0.90
		0.7	0.63, 0.77	0.63, 0.78
CD8 T cell count	0.35	0.8	0.72, 0.89	0.71, 0.91
		0.7	0.63, 0.78	0.62, 0.79
CD56 ^{bright} NK cell count	0.57	0.8	0.68, 0.95	0.65, 0.98
		0.7	0.59, 0.83	0.57, 0.86
T _{reg} count	0.95	0.8	0.60, 1.07	0.57, 1.12
		0.7	0.52, 0.93	0.50, 0.98

ALC = absolute lymphocyte count; CD = cluster of differentiation; CI = confidence interval; LLN = lower limit of normal; NK = natural killer; SD = standard deviation; T_{reg} = T regulatory; vs. = versus.

¹ Common standard deviation for the log-transformed change from Baseline.

² Up to Week 48.

CONFIDENTIAL

The information contained herein may not be used, disclosed, or published without the written consent of Biogen MA Inc.

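### The 90% confidence intervals in the sample-size table do not follow from the stated N = 180, group sizes and SDs; 13 of 16 differ, always printed too wide

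*Protocol*

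**What the plan says.** Protocol Section 16.7 sizes the study on precision of estimation, not on a hypothesis test. SAP Section 4 carries the same text and the same intervals.

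- Evaluable number: "based on a total of 180 evaluable subjects at Week 48".
- Group sizes: "it is expected that approximately 137 subjects will have all ALC values" at or above LLN, and "approximately 43 subjects will have at least 1 ALC value" below LLN.
- Second contrast (at least 2 values below LLN): "historical data suggest that 16% of the patients treated with Tecfidera may have 2 or more ALC values" below LLN in the first 48 weeks. No group size is given; 16% of 180 is 28.8.
- Effect sizes: the intervals are illustrated "using the scenario of a true ratio of 0.8 (20% decrease) and 0.7 (30% decrease), respectively".
- SDs: 0.32 (CD4), 0.35 (CD8), 0.57 (CD56bright NK) and 0.95 (Treg), defined in the table footnote as "Common standard deviation for the log-transformed change from Baseline".
- Link from inputs to table: the text begins "With this sample size, the 90% CIs for the ratio of the 2 subgroups", and the interval columns are headed "90% CI for the Ratio Based on N = 180".

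Neither document gives a formula for the interval, a choice of z or t quantile, or any allowance added to the width.

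**The concern.** With group sizes, a common log-scale SD, a ratio and a confidence level all stated, each interval is fixed apart from the choice of quantile. The printed intervals should therefore be reproducible, and most are not. The table is the study's only quantitative sample-size justification, so a reader cannot confirm that 180 evaluable subjects give the precision shown. The N, the SDs, the quantile or individual limits must differ from what is declared.

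**Working it through.** **Inputs.** 180 × 0.76 = 136.8 (137); 180 × 0.24 = 43.2 (43); 180 × 0.16 = 28.8 (29, derived). SDs and ratios are as printed. The level is two-sided 90%, so z = 1.6449.

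**Formula.** Limits = ratio × exp(± q × SD × √(1/n₁ + 1/n₂)), where q is z, or t with n₁ + n₂ − 2 degrees of freedom.

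- First contrast: √(1/43 + 1/137) = 0.1748.
- Second contrast: √(1/29 + 1/137) = 0.2044.

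**An interval that does reproduce.** CD4, ratio 0.8, first contrast: 1.6449 × 0.32 × 0.1748 = 0.0920, giving 0.730 to 0.877. The table prints 0.73, 0.88.

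**An interval that does not.** Treg, ratio 0.8:

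- First contrast: 1.6449 × 0.95 × 0.1748 = 0.2731, giving 0.609 to 1.051. Printed: 0.60, 1.07. The printed log half-width is ln(1.07/0.60)/2 = 0.289, which is 6% larger.
- Second contrast: 1.6449 × 0.95 × 0.2044 = 0.3194, giving 0.581 to 1.101. Printed: 0.57, 1.12.

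**All sixteen, with z:**

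| Subset, ratio | ≥1 below LLN: printed | computed | ≥2 below LLN: printed | computed |
|---|---|---|---|---|
| CD4, 0.8 | 0.73–0.88 | 0.73–0.88 (match) | 0.71–0.90 | 0.72–0.89 |
| CD4, 0.7 | 0.63–0.77 | 0.64–0.77 | 0.63–0.78 | 0.63–0.78 (match) |
| CD8, 0.8 | 0.72–0.89 | 0.72–0.88 | 0.71–0.91 | 0.71–0.90 |
| CD8, 0.7 | 0.63–0.78 | 0.63–0.77 | 0.62–0.79 | 0.62–0.79 (match) |
| CD56bright, 0.8 | 0.68–0.95 | 0.68–0.94 | 0.65–0.98 | 0.66–0.97 |
| CD56bright, 0.7 | 0.59–0.83 | 0.59–0.82 | 0.57–0.86 | 0.58–0.85 |
| Treg, 0.8 | 0.60–1.07 | 0.61–1.05 | 0.57–1.12 | 0.58–1.10 |
| Treg, 0.7 | 0.52–0.93 | 0.53–0.92 | 0.50–0.98 | 0.51–0.96 |

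With z, 3 of 16 intervals and 12 of 32 limits match. With t, 5 of 16 and 14 of 32 match; the two extra intervals are CD8 at 0.8 and CD56bright at 0.7, both in the first contrast. All 20 (z) or 18 (t) mismatched limits are printed wider than computed. The largest gap is 0.0189 (z) or 0.0172 (t). Taking 28 or 28.8 instead of 29 leaves both interval counts unchanged.

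**Candidate explanations:**

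- *Rounded SDs.* Any SD that rounds to the printed value reaches at most 6 of 16 intervals, and no Treg interval. The four Treg intervals together need an SD of 1.001–1.007 (z) or 0.995–1.002 (t), against 0.95 printed.
- *95% level.* No interval matches.
- *Welch degrees of freedom, or outward rounding with z or pooled t.* 8 to 10 intervals still differ.
- *N = 162 (180 × 0.9; groups 123, 39, 26) with t.* 13 of 16 intervals and 29 of 32 limits match.
- *SDs 5% larger at N = 180.* 13 of 16 and 29 of 32.
- *An 80% assurance allowance on the width at N = 180, with t.* 13 of 16 and 29 of 32.

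The last three fit equally well, so the table cannot distinguish between them.

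**A check that does not depend on N, SD scaling or quantile.** Under any formula of this form, the ratio of the two columns' log half-widths depends only on group sizes when a common quantile is used. At 137, 43 and 29 it is 0.2044/0.1748 = 1.169, and it must be the same for every subset. The half-widths that the printed two-decimal limits allow are:

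- CD4: 0.0975–0.0984 and 0.1123–0.1133, so a ratio of 1.141–1.163.
- CD56bright: 0.1666–0.1699 and 0.2000–0.2080, so a ratio of 1.177–1.249.

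These ranges do not overlap, so no single basis of this form yields the whole table.

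**The case against.** The best reply has four parts.

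1. **Rounding scale.** Counting intervals exaggerates the problem: 29 of 32 limits (z) or 30 of 32 (t) are within one unit in the second decimal, and the table is offered as an illustration with approximate group sizes. This is true and bounds the practical weight. It does not explain why every discrepancy goes the same way, or why all four Treg intervals miss at both limits.

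2. **Unstated method.** No formula is given, so another method could be behind the figures. The t quantile on the smaller group's degrees of freedom, with 28 in the second contrast, keeps N = 180 and the printed SDs and matches 13 of 16 intervals and 28 of 32 limits. But it still misses Treg in the first contrast, and with 29 it matches only 7 of 16. It is one more undocumented candidate.

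3. **The column-ratio check.** It assumes log-symmetric limits and the same group sizes for every subset, and it would pass if one CD4 limit read 0.64 instead of 0.63. Different numbers per assay would contradict the column heading, and changing that one digit concedes that a printed limit is off. Simulated limits are not excluded by the documents, but are not mentioned either.

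4. **Consequence.** SAP Section 2.1 already speaks of treatment in the past tense, so the table can no longer alter recruitment. SAP Section 5.3.1 reports 95% intervals from its model and uses a different comparator for the subgroup with at least 2 low values. This stands: the correction concerns the record of the justification, not the conduct or analysis of the study.

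**Conclusion.** The concern holds. On the stated inputs, 13 of 16 intervals are wrong at two decimals with z and 11 with t, all in the direction of too little precision. The largest gap in a limit is 0.019 (Treg, ratio 0.8, second-contrast upper limit: 1.12 printed, 1.101 computed). The log half-width is 5–6% too large for Treg and about 5% too large on average over the sixteen.

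The effect is small and conservative. No interval changes whether it includes 1, and 180/0.9 = 200 is correct.

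The conclusion rests on the standard two-group interval on the log scale and on about 29 subjects for the 16% group. The cause cannot be determined from the documents. At least one printed limit is off on any single basis of that form with common group sizes and a common quantile.

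**What to change.** Make one of two changes, identically in Protocol Table 6 and SAP Table 3.

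1. **Recompute.** Print the computed columns shown above, and add a footnote giving the formula, the z quantile and the group sizes 137, 43 and 29. If t is preferred, say so; three upper limits then change: CD8 at 0.8 (first contrast) to 0.89, CD56bright at 0.7 (first contrast) to 0.83, and Treg at 0.7 (second contrast) to 0.97.
2. **Document.** If a different N, different SDs or an assurance allowance was used, keep the figures, state that basis and the formula in the table, and correct any limit that basis does not give.

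Leave 137, 43, 180 and 200 as they are unless the sponsor confirms that another N was used. The cost is one set of figures or one footnote in one table of each document, with no change to design, enrolment or analysis.
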